7.3 Selection and Withdrawal of Subjects

Eligibility criteria for this study have been carefully considered to ensure the safety of the study subjects and to ensure that the results of the study are meaningful in relation to the research hypotheses. It is imperative that subjects fully meet all eligibility criteria.

7.4 Replacement of Subjects

Subjects who withdraw will not be replaced.

8. STUDY ASSESSMENTS – PLAN AND METHODS

8.1 Site of Care and Study Conduct

Subjects may be recruited upon presentation in an outpatient psychiatric practice, emergency department, community mental health setting, or psychiatric hospital. The site of care will be either (1) a community mental health/bipolar clinic setting with overnight observation capability and with immediate access to a psychiatric inpatient facility or (2) an inpatient setting. Only sites that have been using ketamine for stabilization of patients with bipolar depression as part of their practice of medicine for at least 12 months will be included as study sites in the trial. Eligible study sites will already have written policies and procedures around the use of ketamine, will be properly licensed by the Drug Enforcement Administration for the storage and use of ketamine, and will have written criteria for ensuring the safety of patients under their care who receive ketamine.

It should be emphasized that dedicated (typically for-profit) psychiatric research facilities whose physicians do not otherwise provide ongoing care to patients with suicidal bipolar depression are not eligible to participate as study sites because of concerns that such facilities may not have adequate clinical experience or resources to ensure patient safety over the course of the study.

The study protocol does not dictate the site of care (inpatient vs. outpatient). That is determined by the treating physician in consultation with the patient and family, based upon assessment of the patient's acuity, the patient's home environment, and other factors that psychiatrists expert in the management of this patient population use in determining the appropriate site of care. It is anticipated that subjects enrolled at C-SSRS level 4 are likely to be managed in the outpatient setting, whereas those enrolled at C-SSRS level 5 will be maintained under continuous professional observation until they have stabilized at a C-SSRS level 3 or lower. Just as site of care is determined by the treating physician, the decision to discharge those subjects who begin in the inpatient setting is entirely up to the study physician, based upon the same protocols and criteria already in place to determine discharge for patients with suicidal bipolar depression. The study sponsor and the study protocol will not influence this decision in any way. The sponsor does require, however, that subjects with C-SSRS level 5 ideation or behavior be under continual professional observation from the time of enrollment and ketamine infusion to the point at which the patient is deemed to have stabilized and is randomly assigned to one of the study arms.

All eligible subjects will receive ketamine infusion according to the procedures in this protocol. All infusions will be conducted in a clinic-like or hospital setting with a licensed anesthetist, standard monitoring equipment, and full emergency backup available. Subjects who experience sufficient improvement and are stable after the ketamine infusion may be hospitalized or discharged at the discretion of the treating physician. Discharge will only be allowed if there is an established support structure and agreement to follow the safety plan whereby sites will contact subjects twice daily for the next week either in person or through a video connection provided by sponsor and then at least weekly through the end of the study to collect study data to support efficacy and safety. The election to follow subjects who respond to initial ketamine on an inpatient or outpatient basis will be made by the treating study physician with the consent of the subject.

Subjects who meet study criteria for relapse at any point during the study will be withdrawn from the study and offered clinically-appropriate treatment as determined by the treating study physician, which may

include inpatient hospitalization, repeated administration of ketamine, electroconvulsive therapy (ECT), or other treatments determined by professional judgment. Subjects who demonstrate therapeutic benefit from experimental drug NRX-101 (DCS+ lurasidone) at study completion may be offered prescribed DCS by their treating psychiatrist.

The Schedule of Study Activities (Table 3) summarizes the frequency and timing of efficacy, PK, and safety measurements applicable to this study. With the exception of post-dose assessments, visit-specific subject-reported outcomes assessments should be conducted or completed before any tests, procedures, or other consultations for that clinic visit to prevent influencing subject perceptions. A recommended order of study procedures will be provided to sites as a separate document.

Actual dates and times of assessments will be recorded in the source documentation and electronic Case Report Form (eCRF).

8.1.1 Study Visits and Assessments

A schedule of study visits and assessments is provided in Table 3 Schedule of Study ActivitiesTable 3

Table 3 **Schedule of Study Activities**

Assessment/Activity	Study Day	Screening Period 48 hrs	Stage 1			Stage 2										Follow Up /ET Day 70
			Ket. Dosing	4 hr	10 hr +2 hours	Day 1	Day 6	Day 7	Day 10	Day 14	Day 21	Day 28	Day 35	Day 42		
						24 hr post dose	+/- 1 day									
Visit Name/No.	Screen	Baseline			1	2	3	4	5	6	7	8	9	10		
Informed Consent		X														
MINI 7.0.2 DSM 5		X														
Demographics		X														
Medical History		X														
Psychiatric History		X														
Physical Exam		X								X				X		
Vital Signs		X	X	X		X		X	X	X	X	X	X	X		
ECG		X				X				X				X		
Concomitant Medications		X	X				X	X	X	X	X	X	X	X		
C-SSRS		X	X	X	X	X	X	X	X	X	X	X	X	X		
Phone Visit*					X		X									
Adverse Events		X	X	X	X	X	X	X	X	X	X	X	X	X		
CHRT—C, SR		X						X		X	X	X	X			
Remote Independent Rater Interview		X**														
CADSS			X	X												
BISS		X	X	X		X		X	X	X	X	X	X	X		
SIBQ			X	X		X		X	X	X	X	X	X	X		
Blood Draw for drug analyses		X				X***				X***				X***		
BARS			X					X	X	X	X	X	X	X		
BPRS			X	X												
PRISE			X	X		X		X	X	X	X	X	X	X		
Chemistry, CBC		X								X				X		
Urine Tox Screen		X								X				X		
Pregnancy Test (Urine)		X								X				X		
Ketamine Infusion			X													
Randomization						X										
Drug Dispensation & Pill Count						X		X		X	X	X	X	X		

*This phone visit should be performed by the site Principal Investigator, or Sub-Investigator. **The independent interview is performed remotely by telephone by independent raters.

***Blood draws for drug analyses 2 hours after the initial dose, prior to administration of NRX-101 on days 14 and 42, and 2 hours after administration of NRX-101 on day 42.

8.1.2 Screening Period

Once subjects agree to participate in the study by signing the informed consent document, a full medical and psychiatric history will be taken and a physical and laboratory examination will be performed, as outlined in the Schedule of Study Activities (Table 3). The screening period may extend for up to 48 hours following the signing of the informed consent in order to allow time for the independent third party raters' interview to be conducted and the ketamine infusion to be scheduled. Upon determination by the site investigator(s) that the subject meets the inclusion and exclusion criteria for the study, a remote interview will be scheduled with an independent rater.

8.1.3 Remote Interview

To ensure that appropriate subjects are entered into the trial, remote diagnostic assessments (for Bipolar Disorder, C-SSRS and BISS) will be performed by remote, independent third party raters'. The interview will be performed remotely by the independent, third party rater, via telephone during the 24 hour screening period. Depending on level of suicidal ideation and behavior, the subject may be contacted while at home or while being managed in an ED, hospital, or other acute care facility. Sites will be notified of the results within 2 business hours of the interview completion.

8.1.4 Stage 1: Ketamine Infusion

For entry into Stage 1 of the study (ketamine infusion), all eligibility criteria MUST continue to be met (i.e., all inclusion criteria and no exclusion criteria).

All subjects will receive ketamine by continuous infusion for 40 minutes by use of an electronic pump. The start and stop times of the ketamine infusions will be documented in the eCRF.

Detailed instructions for dose preparation will be provided to site research pharmacists in an additional guidance document. Storage conditions should be followed according to the package insert. Dosing procedures will be provided to the clinical unit in a separate infusion document.

Assessments: During the infusion, the Clinician Administered Dissociative Symptom Scale (CADSS) and the Brief Psychiatric Rating Scale (BPRS) are administered at 0 (-5 minutes), 40 minutes (completion of infusion) and 4 hours. Both are administered by a clinician.

Physiological Monitoring: Each participant will be allowed to rest in a semi-recumbent position. Each subject will receive an intravenous (IV) line. The monitoring will include a non-invasive blood pressure cuff, a 3- or 5-lead ECG, a pulse oximeter and oxygen by face mask or nasal cannula at 4 to 6 liters per minute, as needed. Vital signs will be monitored continuously and recorded every 20 minutes. Each subject will receive an infusion for 40 minutes.

The IV line will be left in place for at least 1 hour following the infusion to allow for additional medications to control emergent side effects. Medical staff monitoring the infusion will be prepared to treat increases in blood pressure greater than 180/100 mmHg or heart rate greater than 110 bpm, or follow their institutional guidelines if more conservative. If these elevations resolve spontaneously within a short time period, they will generally not be treated. The study

infusion will be discontinued in the event that three consecutive measurements remain above protocol-defined limits for 20 minutes or more, or according to institutional guidelines if more conservative, despite antihypertensive administration. The psychiatry research staff member will administer rating scales at -5, 40 minutes and 4 hours. All side effects and vital parameters will be recorded during the infusion and for the 4 hours following at 1 hour intervals. Clinically relevant vital sign changes will be recorded as AEs. The subject may be released after the 4 hour measurements are complete as long as they have achieved pre-treatment vital signs measurements or are deemed to be clinically stable” or something along those lines.. Subjects will be required to have an adult escort them home post-administration of ketamine, or may be transported home by a medical transport company provided that presence of a responsible adult at the home location has been verified. Participants who cannot ensure a reliable adult transport or home observer will not be allowed to enroll in the study. Subjects will be instructed not to drive or operate heavy machinery for at least 24 hours post-administration.

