7.1 Inclusion Criteria

1. Male or female, 18 to 65 years of age, inclusive, at screening.
2. Able to read, understand, and provide written, dated, informed consent prior to screening. Participants will be deemed likely to comply with study protocol and communicate with study personnel about AEs and other clinically important information.
3. Diagnosed with BD according to the criteria defined in the DSM-5. The diagnosis of BD will be made by a site psychiatrist and supported by the MINI 7.0.2. The diagnosis will be confirmed by remote, independent raters via teleconference between the screen visit and the baseline visit.
4. Suicidal ideation or behavior of sufficient severity to meet the requirements for a score of 4 or 5 on the C-SSRS.
5. A score equal to or greater than 20 on the MADRS items of the BISS.
6. In good general health, as ascertained by medical history, physical examination (PE) (including measurement of seated vital signs), clinical laboratory evaluations, and electrocardiogram (ECG).
7. If female, a status of non-childbearing potential or use of an acceptable form of birth control per the following specific criteria:
 - c. Non-childbearing potential (e.g., physiologically incapable of becoming pregnant, i.e., permanently sterilized [status post hysterectomy, bilateral tubal ligation], or is post-menopausal with her last menses at least one year prior to screening); or
 - d. Childbearing potential, and meets the following criteria:
 - iv. Childbearing potential, including women using any form of hormonal birth control, on hormone replacement therapy started prior to 12 months of amenorrhea, using an intrauterine device (IUD), having a monogamous relationship with a partner who has had a vasectomy, or is sexually abstinent.
 - v. Negative urinary pregnancy test at screening, confirmed by a negative urinary pregnancy test at randomization prior to receiving study treatment.
 - vi. Willing and able to continuously use one of the following methods of birth control during the course of the study, defined as those which result in a low failure rate (i.e., less than 1% per year) when used consistently and correctly: implants, injectable or patch hormonal contraception, oral contraceptives, IUD, double-barrier contraception, sexual abstinence. The form of birth control will be documented at screening and baseline.
8. Body mass index between 18-35 kg/m².

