8.2.5.2.3. Other Safety Measures

It is expected that some subjects in both groups (more among those randomized to placebo+lurasidone and placebo) will have recurrence of their depression and, possibly suicidality. Therefore, the investigators plan to effect careful surveillance of all study subjects as follows:

Subjects who receive ketamine will be maintained under continuous professional observation until stabilization is documented or ketamine is deemed not to have achieved stabilization and the treating physician has elected another therapeutic option (which in most cases will be hospitalization with ECT). In general, study subjects will be maintained under direct observation in a mental health center or inpatient setting during the 24 hour stabilization period. At the election of the treating physician in consultation with the patient and family, patients may return home during the 24 hour stabilization period, provided the treating physician has made

arrangements with the patient and family to maintain close professional contact during this period and a responsible adult will be escorting the patient at all times. Participants who cannot ensure a reliable adult transport will not be allowed to enroll in the study. Subjects will be instructed not to drive or operate heavy machinery for at least 24 hours post-administration.

Daily contact with a physician, psychologist, or psychiatric nurse who will assess symptoms and any subject or family/significant other concerns. The contact will be either through a telephone or actual visit. All on-site study visits will include a meeting with a study psychiatrist.

The study will employ the use of HIPAA-compliant, electronic video monitoring of medication compliance, with the capability to send an immediate alert for outreach with any missed doses of medication. A non-adherence period of 12 hours (i.e. 2 missed doses will trigger outreach by study personnel).

In case of loss of phone contact or repeated non-adherence to medication, study staff will contact an identified family member/significant other. If study staff determines that hospitalization is urgent, either the family member will take the subject to the emergency room or the staff will contact 911 for an ambulance.

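### For subjects enrolled at C-SSRS level 5, the 4-hour release rule in 8.1.4 (with an unfinished clause) and the go-home exception in 8.2.5.2.3 contradict the observation requirement in 8.1

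*Combined protocol and SAP*

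**What the plan says.** Three sections of the protocol govern where a subject may be between the ketamine infusion and the 24-hour visit.

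- **8.1, Site of Care and Study Conduct.** The choice between inpatient and outpatient care is left to the treating physician, with one stated exception. The sponsor requires that "subjects with C-SSRS level 5 ideation or behavior be under continual professional observation from the time of enrollment and ketamine infusion", and this continues until the subject is judged stabilized and is assigned to an arm. Slightly earlier, the section contrasts level 4 subjects, expected to be mostly outpatients, with level 5 subjects: "whereas those enrolled at C-SSRS level 5 will be maintained under continuous professional observation until they have stabilized at a C-SSRS level 3 or lower". A later paragraph limits discharge after the infusion to subjects who have improved sufficiently and are stable. They must also have a support structure and agree to a safety plan under which the site contacts them twice daily for the next week.
- **8.1.4, Stage 1: Ketamine Infusion.** "The subject may be released after the 4 hour measurements are complete as long as they have achieved pre-treatment vital signs measurements". The sentence goes on to offer clinical stability as an alternative and closes with "or something along those lines". Then: "Subjects will be required to have an adult escort them home post-administration of ketamine", or medical transport may be used if a responsible adult is verified to be at home.
- **8.2.5.2.3, Other Safety Measures.** "Subjects who receive ketamine will be maintained under continuous professional observation until stabilization is documented", or until ketamine is judged to have failed and another option has been chosen. In the same paragraph, at the physician's election, "patients may return home during the 24 hour stabilization period", provided that close professional contact is arranged and a responsible adult accompanies the patient throughout.

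Level 5 subjects are eligible. Section 7.1 asks for "Suicidal ideation or behavior of sufficient severity to meet the requirements for a score of 4 or 5 on the C-SSRS".

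**The concern.** Section 8.1.4 is the text that site staff will have in hand on the infusion day. Its two release conditions are joined by an or, so recovery of vital signs is enough on its own, subject to the escort or home-observer condition. It contains no C-SSRS condition, although Table 3 schedules a C-SSRS at 4 hours. It says nothing about level 5 and does not refer to 8.1. The second condition is visibly unfinished, and clinical stability is not defined there, so two sites could apply it differently.

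At stake is a safety requirement that the sponsor has written in mandatory terms. A site that relies on 8.1.4 as printed can release a subject whom 8.1 says must stay under professional observation, at a time when response to ketamine has not yet been formally assessed.

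**Working it through.** The plan gives no figure to reproduce here. The check compares the texts, with one subtraction.

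**Step 1. The rules side by side.**

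| Section | Applies to | Observation ends, or release is allowed, when | Mentions level 5? | Refers to 8.1? |
|---|---|---|---|---|
| 8.1, sponsor requirement | Level 5 | Judged stabilized and randomized | Yes | – |
| 8.1, discharge conditions | Subjects given ketamine | Improved and stable, with support structure, safety plan and twice-daily contact | No | – |
| 8.1.4 | Subjects given ketamine | 4-hour measurements done, and vital signs recovered or clinically stable (unfinished), with escort or verified adult at home | No | No |
| 8.2.5.2.3, opening | Subjects given ketamine | Stabilization documented, or ketamine failed and another option chosen | No | No |
| 8.2.5.2.3, exception | Subjects given ketamine | Physician elects return home within the 24 hours, with close contact and an adult escort | No | No |

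**Step 2. When the 8.1 requirement ends.** Section 8.1.6 places randomization after an in-person response assessment at 24 hours. A level 5 subject therefore remains under the sponsor requirement until about 24 hours at the earliest.

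**Step 3. When 8.1.4 allows release.** From completion of the 4-hour measurements. Section 8.1.5 shows that early discharge is expected in practice, because the 10-hour contact may be a call to the subject at home.

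**Step 4. Length of the disagreement.** 24 h − 4 h = 20 h. This is a nominal maximum for a subject released at the first opportunity. It is shorter if release comes later.

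**Step 5. Do the other conditions remove the conflict?** An adult escort, a verified adult at home and close telephone or video contact are safeguards. They are not continual professional observation, which is what 8.1 requires for level 5. The discharge conditions in 8.1 do not lift that requirement either.

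**Step 6. Who is affected.** The firm conflict covers level 5 entrants only. For level 4, 8.1 itself expects mostly outpatient care. The documents do not state what share will enter at level 5, so the number of subjects cannot be derived.

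**The case against.** The best defence is that 8.1.4 only permits. It says a subject may be released, in a paragraph about infusion monitoring and vital signs, and can be read as a minimum condition on top of 8.1. A site that keeps its level 5 subjects until randomization complies with both sections. On this view the defect is a missing carve-out and cross-reference. Section 8.2.5.2.3 can likewise be read as a default with a conditional exception. Part of this stands: a breach arises only where a site applies 8.1.4 or the exception without 8.1. But no text says that 8.1 takes precedence, and its level 5 requirement is written as a limit on physician discretion, so exercising that discretion under another section cannot satisfy it. The unfinished clause is a defect on any reading.

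Some stronger inferences are tempting, and the documents do not support them:

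- **That a subject still at level 5 at 4 hours with normal blood pressure may go home under the protocol as a whole.** That follows only if 8.1.4 is read alone. The discharge conditions in 8.1 (sufficient improvement, stability, support, safety plan) would bar it.
- **That a released subject goes many hours without contact, apart from the 10-hour call.** That counts Table 3 only. Section 8.1 adds twice-daily contact after discharge, and 8.2.5.2.3 adds close professional contact and an accompanying adult.
- **That the expected ketamine non-responders (30% of the 177 Stage 1 completers in 13.8.2, 177 × 0.30 ≈ 53) count the subjects at risk.** They include level 4 entrants, and subjects who miss only the depression criterion with a C-SSRS of 3 or lower.
- **That the response assessment or randomization is distorted.** Every subject has the same in-person 24-hour assessment, and some variation in site of care is intended by 8.1.

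**Conclusion.** The contradiction is real, and the text is wrong as written. For subjects enrolled at level 5, 8.1 requires professional observation until randomization, while 8.1.4 and the exception in 8.2.5.2.3 allow them home before that, with no level 5 carve-out and no reference to 8.1. The disagreement lasts up to about 20 hours per subject. This rests on reading 8.1 as running to randomization after the 24-hour assessment, and on release at the earliest time 8.1.4 allows. Section 8.1 itself also describes the end of level 5 observation as reaching a C-SSRS of 3 or lower. If that were the operative end point, the gap would be shorter for subjects who reach it early, which is one more thing the reconciliation should settle.

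Independently of this, one of the two release criteria in 8.1.4 is leftover drafting text. The finding does not extend firmly to level 4 subjects, and it carries no estimate of the number of subjects involved.

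**What to change.** Reconcile 8.1, 8.1.4 and 8.2.5.2.3 so that they state one consistent release and observation rule for the period from infusion to randomization, and say explicitly how subjects enrolled at level 5 are handled. Replace the unfinished clause in 8.1.4 with the criterion the sponsor intends. Make clear in 8.1.4 whether the discharge conditions in 8.1 apply, and cross-refer the three sections. Which rule applies is a decision for the sponsor's clinicians.

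The cost is a wording amendment. Sample size and analysis are unaffected. If the sponsor's decision is that level 5 subjects stay until randomization, some would remain up to about 20 hours longer than 8.1.4 now allows, at sites that 8.1 already requires to be inpatient or capable of overnight observation.
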